## **7.0 DOSE DELAYS/DOSE MODIFICATIONS**

Once a patient undergoes a dose modification, neither CB-839 nor capecitabine may be re-escalated in that patient.

Dose reductions may be implemented for either one agent or both agents depending on the treating physician's assessment of causality.

Patients requiring > 2 dose modification will be taken off protocol therapy.

Patients must receive at least 75% of the total assigned CB-839 and capecitabine doses in order to be evaluable for a DLT in the phase I portion of the study. Missed doses must be for reasons other

than toxicity.

For patients in the phase I portion of the study, dose reductions of CB-839 and capecitabine will be permitted during the first cycle (21 days) only if a patient experiences a toxicity that results in a DLT. If a patient experiences a DLT, treatment continuation at a lower dose of CB-839 and/or capecitabine will be permitted as long as the toxicity has returned to  $\leq$  Grade 1 or baseline within 14 days. Upon recovery, patients may restart at one CB-839/capecitabine dose level lower. Patients who do not recover within 14 days will not be eligible for resumption of treatment with CB-839 or capecitabine.

After cycle 1, dose reductions or interruptions for adverse events may take place at any time at the discretion of the Principal Investigator. Dose interruptions for grade 2 non-hematologic toxicity for up to 5 days can be implemented at the discretion of the treating physician to manage clinically significant toxicity. No dose reduction is required when resuming treatment. Dose interruptions of  $>$  5 days should be discussed with the PI. Patients whose dose is interrupted for  $>$  21 days for any reason must be withdrawn from the study unless prior approval from the PI has been obtained for study continuation.

Adequate medical management for reversible symptoms using supportive medications must be used prior to making a dose modification for these symptoms.

## 7.1 CB-839 Dose Modifications

CB-839 will be initiated at the dose per the assigned dose level and will be given in combination with capecitabine twice daily throughout the 21 day treatment cycle.

### 7.1.1 CB-839 Dose Modification Table

Starting CB-839 dose (mg) by mouth twice daily	1 st Dose Modification (mg) by mouth twice daily	2 nd Dose Modification (mg) by mouth twice daily
400	200	discontinue
600	400	200
800	600	400

### 7.1.2 Hematologic and Non-Hematologic Toxicities (except for liver function changes)

Toxicity Grade	CB-839 Dose Changes During Current Treatment Period	Dose Adjustments for Resumption of Treatment
2 (or, for baseline grade 2, worsening to grade 3)	Hold study drug and provide supportive care	Restart at the same dose level upon resolution to $\leq$ Grade 1 or baseline
3 or 4	Hold study drug and provide supportive care	Reduce to the next lower dose level upon resolution of $\leq$ Grade 1 or

		baseline  If symptoms persist for > 14 days despite dose interruption, the patient must be withdrawn from the study
--	--	---

### 7.1.3 Abnormal liver function tests (AST, ALT, bilirubin)

Grade	CB-839 Modification
1	No change in dose
2	Reduce CB-839 to the next lower dose level
≥ 3	Hold CB-839 until ≤ Grade 1 and resume at the next lower dose level
≥ 3 after resumption of treatment	Hold CB-839 until ≤ Grade 1 and resume at the next lower dose level

### 7.1.4 Non-hematologic Toxicity

For other non-hematologic toxicities, dose reductions of CB-839 will be at the discretion of the investigator. A dose reduction of 200 mg must be performed with each dose reduction. A maximum of 2 dose reductions are permitted.

## 7.2 Capecitabine Dose Modifications

Capecitabine will be initiated at the dose per the assigned dose level and will be given twice daily for the first 14 days out of a 21 day treatment cycle.

Dose modifications should be made according to the following table:

### 7.2.1 Dose Modification Table

Toxicity Grade	During a Course of Therapy	Dose Adjustment for Next Cycle (% of starting dose)
Grade 1	Maintain dose level	Maintain dose level
Grade 2		
1 st appearance	Interrupt until resolved to grade 0-1	100%
2 nd appearance	Interrupt until resolved to grade 0-1	75%
3 rd appearance	Interrupt until resolved to grade 0-1	50%
4 th appearance	Discontinue treatment permanently	
Grade 3		
1 st appearance	Interrupt until resolved to grade 0-1	75%
2 nd appearance	Interrupt until resolved to grade 0-1	50%
3 rd appearance	Discontinue treatment permanently	

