**Hematologic DLT:**

- Grade 4 neutropenia [absolute neutrophil count (ANC)  $< 0.5 \times 10^9/L$ ]
- Grade 3 febrile neutropenia (ANC  $< 1.0 \times 10^9/L$  with a fever  $\geq 38.3$  degrees C)
- Grade 4 thrombocytopenia ( $< 25.0 \times 10^9/L$ )
- Grade  $\geq 3$  thrombocytopenia associated with Grade  $\geq 3$  bleeding

In addition, any other AE that is felt to be treatment-limiting in the medical opinion of the Principal Investigator may be considered a DLT.

Management and dose modifications are outlined in Section 7.

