## 7.2.2 Hematologic Toxicities

ANC (/mm^3)		Platelets (/mm^3)	Modification
< 1500/mm 	and/or	< 100,000/mm 	Hold until ANC ≥ 1500/mm  and platelets are ≥ 100,000/mm  , resume per dose modification table
≥ 1500/mm 	and	≥ 100,000/mm 	No dose modification

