## 7.2.3 Nausea and Vomiting

\*\*Adequate medical management for these conditions should be implemented before a dose modification is made for one of these symptoms\*\*

Grade	Modification
1	No change in dose
2	Hold until ≤ grade 1; resume at same dose level
3	Hold until ≤ 1; resume per dose modification table
4	Off protocol therapy

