## 7.2.4 Mucositis, Diarrhea and Esophagitis

\*\*Adequate medical management for these conditions should be implemented before a dose modification is made for one of these symptoms\*\*

Grade	Toxicities/Symptoms	Modification
1	Mucositis, esophagitis or diarrhea	No dose modification
2	Diarrhea	No dose modification
2	Mucositis or esophagitis	Hold until ≤ grade 1 and resume per dose modification table
3	Diarrhea	Hold until ≤ grade 1; resume per dose modification table
3/4	Mucositis or esophagitis	Hold until ≤ grade 1; resume per dose modification table

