#### 7.2.6 Hyperbilirubinemia

If grade 3 or 4 hyperbilirubinemia occurs that is thought to be related to capecitabine, capecitabine should be held until the bilirubin improves to  $\leq 3.0 \times$  institutional ULN. When ready, resume capecitabine according to the capecitabine dose modification table (Section 7.2.1) where each episode of grade 3 toxicity results in a dose modification. Discontinue treatment permanently for the third grade 3 incident. If the patient has already had a dose modification for another toxicity, the new dose level should be used as the baseline for making these adjustments.

For grade 4 toxicity, resume capecitabine at 50% of the original starting dose for the first incident and discontinue treatment permanently for any subsequent incident. If the patient has already had a dose modification for another toxicity, the new dose levels should be used as the baseline for making these adjustments.

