### 7.2.7 Non-hematologic Toxicity

For other non-hematologic toxicities, dose reductions of capecitabine will be at the discretion of the investigator. Dose modification should be made according to the dose modification table. A maximum of 2 dose reductions are permitted.

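### Capecitabine table 7.2.1 stops at grade 3, so phase II has no stated restart dose after grade 4 cytopenia, mucositis, esophagitis or diarrhea

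*Combined protocol and SAP*

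**What the plan says.** Section 7.2 makes table 7.2.1 the governing rule for capecitabine changes. The table is a lookup by grade and by number of appearances, and its last column is headed "Dose Adjustment for Next Cycle (% of starting dose". The rows are grade 1, grade 2 (first to fourth appearance) and grade 3 (first to third appearance: 75%, 50%, stop). Nothing follows grade 3, and that block is not labelled as grade 3 or higher.

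Other sections point to the table:

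- 7.2.2 holds capecitabine for any ANC below 1500/mm³ and/or platelets below 100,000/mm³, then says "resume per dose modification table". It sets no lower limit.
- 7.2.4 has a row labelled 3/4 for mucositis or esophagitis: "Hold until ≤ grade 1; resume per dose modification table". Its diarrhea rows end at grade 3.
- 7.2.7, for other non-hematologic toxicities, leaves reductions to the investigator and adds: "Dose modification should be made according to the dose modification table".

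Grade 4 is settled for some events. For nausea or vomiting, 7.2.3 says "Off protocol therapy". For bilirubin, 7.2.6 says "For grade 4 toxicity, resume capecitabine at 50% of the original starting dose for the first incident", with a permanent stop at any later incident. For a phase I cycle 1 dose-limiting toxicity, 7.0 allows a restart one dose level down after recovery. Section 6.6 lets the investigator take a patient off for safety.

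**The concern.** A rule that refers to a missing table entry cannot be followed as written. After recovery from grade 4 neutropenia, thrombocytopenia, mucositis or esophagitis, the site is told to look up a percentage that is not there. The nearest entry is the first grade 3 row, at 75%. The two rules the protocol writes specifically for grade 4 capecitabine toxicity, in 7.2.3 and 7.2.6, are both stricter than that.

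The stake is patient safety and consistency between sites. The events affected are among the most serious the protocol grades, and a site that falls back on the grade 3 row would re-expose the patient to more drug than the protocol accepts after its own grade 4 examples. CB-839 does not have this gap: 7.1.2 has a row for grades 3 and 4 together and states the action. After the same grade 4 neutropenia, the CB-839 restart dose is therefore fixed and the capecitabine restart dose is not.

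**Working it through.** There is no sample size, power or error rate to reproduce. The check compares each capecitabine rule with the table it relies on.

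**Do grade 4 counts fall inside 7.2.2?** Section 6.4 lists "Grade 4 neutropenia [absolute neutrophil count (ANC" below 0.5 × 10⁹/L) and grade 4 thrombocytopenia below 25 × 10⁹/L as dose-limiting. One litre is 10⁶ mm³, so these are 0.5 × 10⁹ / 10⁶ = 500/mm³ and 25 × 10⁹ / 10⁶ = 25,000/mm³. Both lie below the 7.2.2 limits of 1500 and 100,000, so both go to the table.

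**Is a restart dose stated after grade 4?** (Phase II, and phase I after cycle 1.)

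| Grade 4 event | Section | Instruction | Dose stated? |
|---|---|---|---|
| Neutropenia, thrombocytopenia | 7.2.2 | hold, then table | No |
| Mucositis, esophagitis | 7.2.4 | hold, then table | No |
| Diarrhea | 7.2.4 | no row | No |
| Other non-hematologic | 7.2.7 | investigator discretion, and table | No |
| Nausea, vomiting | 7.2.3 | off therapy | Yes |
| Hyperbilirubinemia | 7.2.6 | 50%, then stop | Yes |

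**Do the general rules supply a dose?**

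- 7.0 bars re-escalation, which sets no level. Its general discretion sentence, "After cycle 1, dose reductions or interruptions for adverse events may take place at any time at the discretion of the Principal Investigator", gives no percentage.
- 6.2 caps the reduced levels at 80% and 55% of the initial dose and refers to 7.2. It does not say which level follows grade 4.
- 6.6 covers removal from treatment, not the dose on restart.

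**Size of the gap for a first grade 4 event.** The phase II start (6.2.2) is 1000 mg/m² twice daily, which is 2000 mg/m²/day, or 2000 × 14 = 28,000 mg/m² per course.

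- Read as first grade 3 (75%): 2000 × 0.75 = 1500 mg/m²/day; × 14 = 21,000 per course.
- Read as in 7.2.6 (50%): 2000 × 0.50 = 1000 mg/m²/day; × 14 = 14,000 per course.
- Read as in 7.2.3 (stop): 0.

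The ratio of the two restart doses is 1500 / 1000 = 1.5.

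**The case against.** The strongest defence is that the protocol leaves such decisions to clinical judgement and surrounds them with checks. The discretion sentence in 7.0 begins after cycle 1, but the table sets the dose for the next cycle, so a reduction prompted by a cycle 1 event falls within that discretion. Section 7.0 also asks that interruptions longer than 5 days be discussed with the principal investigator, and requires withdrawal after 21 days unless that investigator has agreed otherwise. With the safety criterion in 6.6, no site is obliged to re-treat after a dangerous event. All of this stands, and it rules out any inference that patients must be restarted or that sites act unchecked. It does not supply a dose, and 7.2.2 and 7.2.4 send the site to the table without mentioning discretion.

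A second defence is that the protocol often groups grade 4 with grade 3: the 3/4 row in 7.2.4, the row for grade 3 and above in 7.2.5, and the row for grades 3 and 4 in 7.1.2. Using the grade 3 entry for mucositis is then a fair reading. It still gives 75%, against 50% or a stop in the capecitabine rules specific to grade 4. It does nothing for diarrhea, which has no such row.

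Two stronger readings are tempting, and neither is supported.

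- A reader might infer that no grade 4 toxicity has a capecitabine rule. Sections 7.2.3, 7.2.6 and, for phase I cycle 1, 7.0 show otherwise.
- A reader might infer that the gap decides who is replaced under 3.3.2, and so who counts among the 18 or 40. Suppose the event follows a complete first course. By milligrams, week 9 exposure is (1 + 0.75 + 0.75)/3 = 83.3% at the 75% restart and (1 + 0.5 + 0.5)/3 = 66.7% at the 50% restart, on either side of the 75% threshold. By number of doses both are 100%. Section 3.3.2 does not say which count applies, so that contrast rests on a separate ambiguity. Stopping gives 1/3 = 33.3% on either count, but 6.6 allows stopping whatever the table says. With no grade 4 rates, no effect on the sample can be estimated.

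Finally, a row lost in converting the PDF to text cannot be wholly excluded. It is unlikely: the grade 3 block ends cleanly, the 7.1.2 table keeps its continuation across a break, and 7.2.6 writes out its own grade 4 rule instead of citing a row.

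**Conclusion.** The point holds in limited form. In phase II, and in phase I after cycle 1, no text gives the capecitabine restart dose after grade 4 neutropenia, thrombocytopenia, mucositis, esophagitis or diarrhea. Other non-hematologic grade 4 events meet the same empty entry, softened by the discretion in 7.2.7. Section 1.4 reports phase I fully accrued, so the practical weight falls on phase II.

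The possible daily doses are 1500, 1000 or 0 mg/m². The default most likely to be used is the highest, and it is laxer than both capecitabine rules the protocol writes specifically for grade 4. This assumes that the dose modification table named in 7.2.2 and 7.2.4 is table 7.2.1, as 7.2.6 states by number for its own case, and that the table is complete as published. It is a safety clarification worth making. It does not touch the two-stage design or its error rates.

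**What to change.** Add to table 7.2.1:

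- *Grade 4, first appearance:* interrupt until grade 0-1, then 50% of starting dose; discontinue permanently if already at 50% or below, or if the investigator judges a restart unsafe.
- *Grade 4, second appearance:* discontinue permanently.

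Keep 7.2.3 and 7.2.6 as event-specific rules, and add a grade 4 diarrhea row to 7.2.4 that points to the new entry. The 50%-then-stop pattern follows 7.2.6, stays under the 55% ceiling in 6.2 and never raises a dose, as 7.0 requires. Section 7.2.6 is written for bilirubin only, so extending its level to other events is a clinical choice. Stopping after any grade 4 event, as in 7.2.3, would also close the gap. What matters is that one rule is written down.

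The cost is one grade 4 block in 7.2.1 and one row in 7.2.4 at the next amendment, with no added patients, visits or procedures.

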## 7.2.2 Hematologic Toxicities

ANC (/mm^3)		Platelets (/mm^3)	Modification
< 1500/mm 	and/or	< 100,000/mm 	Hold until ANC ≥ 1500/mm  and platelets are ≥ 100,000/mm  , resume per dose modification table
≥ 1500/mm 	and	≥ 100,000/mm 	No dose modification

## 7.2.3 Nausea and Vomiting

\*\*Adequate medical management for these conditions should be implemented before a dose modification is made for one of these symptoms\*\*

Grade	Modification
1	No change in dose
2	Hold until ≤ grade 1; resume at same dose level
3	Hold until ≤ 1; resume per dose modification table
4	Off protocol therapy

## 7.2.4 Mucositis, Diarrhea and Esophagitis

\*\*Adequate medical management for these conditions should be implemented before a dose modification is made for one of these symptoms\*\*

Grade	Toxicities/Symptoms	Modification
1	Mucositis, esophagitis or diarrhea	No dose modification
2	Diarrhea	No dose modification
2	Mucositis or esophagitis	Hold until ≤ grade 1 and resume per dose modification table
3	Diarrhea	Hold until ≤ grade 1; resume per dose modification table
3/4	Mucositis or esophagitis	Hold until ≤ grade 1; resume per dose modification table

## 7.2.5 Palmar-Plantar Erythrodysesthesia Syndrome (Hand and Foot Rash)

Grade	Modification
1	No dose modification
2	Hold until symptoms resolve to grade 0 or 1. Resume per dose modification table.
≥ 3	Hold until symptoms resolve to grade 0 or 1. Resume per dose modification table.

#### 7.2.6 Hyperbilirubinemia

If grade 3 or 4 hyperbilirubinemia occurs that is thought to be related to capecitabine, capecitabine should be held until the bilirubin improves to  $\leq 3.0 \times$  institutional ULN. When ready, resume capecitabine according to the capecitabine dose modification table (Section 7.2.1) where each episode of grade 3 toxicity results in a dose modification. Discontinue treatment permanently for the third grade 3 incident. If the patient has already had a dose modification for another toxicity, the new dose level should be used as the baseline for making these adjustments.

For grade 4 toxicity, resume capecitabine at 50% of the original starting dose for the first incident and discontinue treatment permanently for any subsequent incident. If the patient has already had a dose modification for another toxicity, the new dose levels should be used as the baseline for making these adjustments.

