**Non-Hematologic DLT:**

- $\geq$  Grade 3 non-hematologic toxicity according to the Common Terminology Criteria for Adverse Events (CTCAE) version 4 *except the following:*
  - Nausea, vomiting, or diarrhea lasting < 48 hours and controlled by optimal antiemetic/antidiarrheal therapy
  - Grade 3 hyperglycemia lasting < 72 hours with standard anti-diabetic therapy
  - Clinical laboratory abnormalities that are reversible to  $\leq$  Grade 1 or baseline status within 72 hours with outpatient care and/or monitoring, or that are considered not clinically significant by the Principal Investigator
- Grade 4 hyperglycemia ( $>500$  mg/dL; 27.8 mmol/L; life threatening consequences)
- Grade 4 hypoglycemia ( $<30$  mg/dL;  $<1.7$  mmol/L; life threatening consequences)
- Grade 4 AST ( $>20.0$  x the upper limit of normal)
- Grade 4 ALT ( $>20.0$  x the upper limit of normal)
- Grade 3 AST or ALT elevation ( $>5.0 - 20.0$  x the upper limit of normal;  $>5$  x the upper limit of normal for  $>2$  weeks) with concomitant Grade 2 increase in total bilirubin ( $>1.5 - 3.0$  x the upper limit of normal)

Events involving elevation in the AST, ALT or bilirubin with a clear alternative explanation (such as progressive disease within the liver) can be exempt from being considered a DLT-defining event.

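### After a first or second grade 3 hyperbilirubinemia, Section 7.2.6 lets capecitabine resume at a bilirubin level where the table in 7.2.1 still interrupts it, and no precedence is stated

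*Combined protocol and SAP*

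**What the plan says.** Four places in the protocol bear on this.

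- **Section 7.2.6 (capecitabine, hyperbilirubinemia).** For a grade 3 or 4 event thought to be related to capecitabine, "capecitabine should be held until the bilirubin improves to" 3.0 times the institutional ULN or lower. The section then points elsewhere: "When ready, resume capecitabine according to the capecitabine dose modification table (Section 7.2.1"). It adds that each grade 3 episode leads to a dose modification, that the third grade 3 incident ends treatment, and that grade 4 events follow a separate rule in its second paragraph.
- **Section 7.2 and table 7.2.1 (capecitabine, general).** The table is introduced with "Dose modifications should be made according to the following table". For the first and second grade 3 appearance, and for the first three grade 2 appearances, the instruction during therapy is "Interrupt until resolved to grade 0-1". There is no grade 4 row.
- **Section 6.4 (non-hematologic dose-limiting toxicity).** One criterion is a grade 3 AST or ALT elevation "with concomitant Grade 2 increase in total bilirubin", and the limits printed beside it put grade 2 bilirubin above 1.5 and up to 3.0 times ULN.
- **Section 7.1.3 (CB-839, liver tests including bilirubin).** For grade 3 or higher: "Hold CB-839 until ≤ Grade 1 and resume at the next lower dose level".

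**The concern.** Sections 7.2.6 and 7.2.1 both govern capecitabine, and 7.2.6 names 7.2.1 as the place to go for resumption. Yet the bilirubin level at which 7.2.6 ends the hold lies inside the grade for which 7.2.1 continues the interruption. Two investigators who follow the protocol could act in opposite ways on the same laboratory value.

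The first stake is patient safety, since the disputed instruction is whether to give a drug while an event attributed to it is still resolving. The second is exposure. The length of the hold feeds into the dose-intensity rule for replacing phase II patients in Section 3.3.2. During the disputed period a patient may also receive one of the two drugs alone, although the regimen under test is the combination.

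**Working it through.** No sample-size or error-rate figure is involved, so the check sets the rules side by side on one scale.

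**Step 1: put the rules on a common scale.** Table 7.2.1 and Section 7.1.3 speak in grades, and 7.2.6 speaks in multiples of ULN. Section 6.4 supplies the conversion. Grade 2 runs from above 1.5 to 3.0 times ULN, so grade 0-1 is 1.5 times ULN or lower, and anything above 3.0 is grade 3 or higher. The 7.2.6 ceiling of 3.0 is therefore the top of grade 2, and the grade 0-1 ceiling is 1.5. Ratio: 3.0 / 1.5 = 2.

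**Step 2: follow a patient recovering from a first or second grade 3 event attributed to capecitabine.**

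| Bilirubin (x ULN) | Grade by 6.4 limits | Capecitabine under 7.2.6 | Capecitabine under 7.2.1 | CB-839 under 7.1.3 |
|---|---|---|---|---|
| above 3.0 | 3 or higher | hold | interrupt | hold |
| above 1.5 to 3.0 | 2 | may resume | interrupt | hold |
| 1.5 or lower | 0-1 | may resume | may resume | may resume |

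The two capecitabine columns differ only in the middle row, and they differ across all of it. At 2.5 times ULN, for example, 7.2.6 allows a restart and 7.2.1 does not.

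**Step 3: find which events reach the conflict.** A third grade 3 event ends treatment under both sections, so no restart question arises. A grade 4 event has its own rule in 7.2.6 and no row in 7.2.1, so there is no direct clash. That leaves the first and second grade 3 events.

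**Step 4: look for a precedence rule.** None is stated. The neighboring non-hematologic subsections 7.2.3, 7.2.4 and 7.2.5 require recovery to grade 1 or lower wherever they order a hold. Only 7.2.6 sets a restart level inside grade 2, and it gives no reason.

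**Step 5: see how hold length could matter in phase II.** Section 3.3.2 replaces a patient who takes less than 75% of the planned doses of either drug before the 9-week assessment. Assume that planned doses means the full schedule over three cycles.

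- Capecitabine: 3 x 14 x 2 = 84 doses, and 0.75 x 84 = 63. More than 84 - 63 = 21 missed doses (21 / 2 = 10.5 dosing days) triggers replacement.
- CB-839: 63 x 2 = 126 doses, and 0.75 x 126 = 94.5. More than 31 missed doses (31 / 2 = 15.5 days) triggers replacement.

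A capecitabine hold prolonged by the stricter reading could therefore cross the 75% line before the CB-839 hold does. Section 7.0 also withdraws patients interrupted for more than 21 days without prior approval from the principal investigator. It does not say which drug is meant. If the CB-839 hold counts, that limit could be reached whichever capecitabine rule is used.

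**The case against.** The strongest reply is that 7.2.6 is a specific rule that displaces the general table. Event-specific subsections do depart from it: 7.2.4 makes no change for grade 2 diarrhea, where the table interrupts, and 7.2.3 resumes grade 2 nausea or vomiting at the same dose, where the table steps down on repeat appearances. The cross-reference in 7.2.6 goes on to mention the dose modification for each grade 3 episode, which suggests that the table is being borrowed for the dose step and not for the recovery level. This reading is plausible, and some sites would adopt it. It does not settle the matter. The protocol never says that 7.2.6 replaces the table's recovery condition, the table is presented as the rule for capecitabine, and the sibling hold rules all use grade 1 or lower.

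Three stronger readings are tempting, and the documents do not support them.

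- *That 7.1.3 makes this a three-way contradiction.* It governs a different drug. Section 7.0 says "Dose reductions may be implemented for either one agent or both agents", according to the physician's view of causality. That sentence concerns reductions and not holds, but it shows that separate management is contemplated. The CB-839 hold is an unexplained mismatch between the two drugs and nothing more.
- *That every grade 3 or 4 case is affected.* Grade 4 has no row in the table, some events end treatment, and some patients will not recover or will be withdrawn. Scheduled chemistry in phase II is on days 1, 8 and 15 of cycle 1 and then day 1 of each cycle, so bilirubin can cross the whole band between scheduled draws.
- *That a patient restarted under 7.2.6 must at once be interrupted again under the grade 2 row.* The rows count appearances of a toxicity, and a resolving grade 3 event is not clearly a new grade 2 appearance.

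On frequency the objection also stands. Section 8.1 lists bilirubin elevation on CB-839 among rare events (under 2%), Section 1.2.2 gives 1.5% for grade 3 treatment-related liver-test abnormalities with twice-daily dosing, and Section 1.4 reports no dose-limiting toxicity in 16 phase I patients. No rate is given for grade 3 hyperbilirubinemia attributed to capecitabine.

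**Conclusion.** The point holds in a limited form. For a first or second grade 3 hyperbilirubinemia attributed to capecitabine, 7.2.6 and 7.2.1 give opposite restart instructions whenever bilirubin is above 1.5 and up to 3.0 times ULN, with no stated precedence. Outside that band they agree. In the same band 7.2.6 can lead to capecitabine being given without CB-839, and the protocol does not say whether this is intended.

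The conclusion rests on using the grade limits printed in Section 6.4 to read the grades in 7.2.1 and 7.1.3. The number of patients affected cannot be estimated from the documents and may be small, so the effects on exposure and replacement are possible and not quantified. Nothing here implies that either restart level is unsafe or correct.

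**What to change.** Reconcile Sections 7.2.6 and 7.2.1 so that one recovery level, written both as a grade and as a multiple of ULN, governs restart of capecitabine after hyperbilirubinemia. Alternatively, state expressly which section takes precedence. Add one sentence saying whether capecitabine may restart while CB-839 is still held under 7.1.3 for the same event. The choice of level is the sponsor's.

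The cost is a few lines in one amendment. No new assessment is needed, because total bilirubin is already in the serum comprehensive panel listed under the Section 11.4 calendar.

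### After an earlier capecitabine reduction, 7.2.6 gives two different doses for a first grade 4 hyperbilirubinemia event, and its grade 3 steps run past the two-modification limit in 7.0

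*Combined protocol and SAP*

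**What the plan says.** All doses below are capecitabine in mg/m² twice daily. Section 6.1.2 starts phase II patients at 1000.

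- **7.2.1 (Dose Modification Table)** expresses every step relative to the start, under the column "Dose Adjustment for Next Cycle (% of starting dose". Grade 3 goes to 75%, then 50%, then permanent discontinuation. The table has no grade 4 row.
- **7.0** sets a general limit: "Patients requiring > 2 dose modification will be taken off protocol therapy".
- **7.2.7** sets a similar limit for other non-hematologic toxicities: "A maximum of 2 dose reductions are permitted".
- **7.2.6, grade 3**, sends the site to the 7.2.1 table and says that "each episode of grade 3 toxicity results in a dose modification". It stops late: "Discontinue treatment permanently for the third grade 3 incident". It then adds "If the patient has already had a dose modification for another toxicity, the new dose level should be used as the baseline" for the adjustments.
- **7.2.6, grade 4**, says to "resume capecitabine at 50% of the original starting dose for the first incident and discontinue treatment permanently for any subsequent incident". The next sentence, under the same condition of an earlier modification for another toxicity, says "the new dose levels should be used as the baseline for making these adjustments".

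No section says which rule takes precedence.

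**The concern.** The re-basing sentences matter only for a patient who has already been cut, and for that patient they pull against the rest of the dosing rules.

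The grade 4 paragraph pulls against itself. One sentence fixes the reference as the original starting dose. The next replaces that reference with the reduced dose. The word *original* has work to do only once a dose has changed, which is exactly the case the next sentence covers. The 7.2.1 table cannot arbitrate, because it has no grade 4 row.

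The grade 3 paragraph pulls against 7.0. It calls each episode a dose modification, the term that 7.0 counts, yet it stops only at the third bilirubin incident, whatever cuts came before.

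What is at stake is dosing safety after severe hyperbilirubinemia attributed to capecitabine. Two investigators could resume the same patient at different doses, and one could resume at an unchanged dose after a grade 4 event. Each could point to a sentence in the protocol.

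**Working it through.** **Inputs.** Start 1000 (6.1.2). Steps 75% and 50% of start (7.2.1). More than 2 modifications means off protocol therapy (7.0). One earlier cut puts the patient at 750, two at 500.

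**Formula.** Dose = step fraction × baseline. The baseline is 1000 under 7.2.1 and the already reduced dose under the re-basing sentences. Modification number = earlier capecitabine cuts + bilirubin episodes so far.

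**The plan's own figures first.** With no earlier cut, 7.2.6 gives 0.75 × 1000 = 750, then 0.50 × 1000 = 500, then stop. For grade 4, both sentences give 500. This agrees with 7.2.1 and 7.0, so there is no conflict for an unreduced patient.

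**Grade 4, first incident**

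| Earlier cuts | Half of original dose | Half of reduced dose | Modification no. |
|---|---|---|---|
| 1 (at 750) | 0.50 × 1000 = 500 | 0.50 × 750 = 375 | 2 on either reading; 7.0 is silent |
| 2 (at 500) | 0.50 × 1000 = 500, unchanged | 0.50 × 500 = 250 | none for 500; 3 for 250, so off under 7.0 |

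After one cut the two doses differ by 500/375 = 1.33. After two they differ by 500/250 = 2.

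**Grade 3, re-based**

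| Earlier cuts | Episode | Dose | % of start | Modification no. | 7.0 |
|---|---|---|---|---|---|
| 1 | first | 0.75 × 750 = 562.5 | 56.25 | 2 | continue |
| 1 | second | 0.50 × 750 = 375 | 37.5 | 3 | off |
| 2 | first | 0.75 × 500 = 375 | 37.5 | 3 | off |
| 2 | second | 0.50 × 500 = 250 | 25 | 4 | off |

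The doses 375 and 250 are derived here; 7.2.6 does not print them. Nor does it speak of a third or fourth modification; that comes from counting.

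**In tablets.** Section 6.2's example patient has a BSA of 1.97: 1.97 × 2 × 1000 = 3940 mg/day, dispensed as 4000 (1.5% over). By the same rounding, 500 gives 1970 → 2000 mg/day, 375 gives 1477.5 → 1500, and 250 gives 985 → 1000. Each is 1.5% over and inside the 5% ceiling. A first grade 4 event therefore means 2000 or 1500 mg/day after one earlier cut, and 2000, 1000 or nothing after two.

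**How often.** Section 8.1 puts bilirubin elevation on CB-839 below 2%; 0.02 × 40 = 0.8, so fewer than 0.8 of 40 patients. Section 8.2 lists hyperbilirubinemia for capecitabine without a frequency. The path also needs an earlier cut. No count of affected patients can be given.

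**The case against.** The best defence reads the sections together. Section 7.0 states its limit without exception, and 7.2.6 does not claim to override it. On that reading every grade 3 dose of 375 or 250 falls at a third or fourth modification, so the patient is already off. What remains is redundant text, not opposite treatment. This largely stands, and it is why grade 3 is secondary here. A reader might infer that the protocol authorises dosing at 37.5% or 25% of start. The documents do not support that: it would need 7.2.6 to displace 7.0, and nothing says it does. A reader might also take 50% as a stated minimum dose. Section 7.2.1 only lists steps and sets no floor, the percentages in 6.2 are rounding ceilings, and 7.2.7 covers other toxicities.

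For grade 4, the second sentence can be read as an exception to the first, giving 375 after one cut and, through 7.0, off after two. That is a reasonable reading, and under it the unchanged dose disappears. But it leaves *original* with nothing to do, and the text does not call the second sentence an exception. After one cut, 500 or 375 stays open.

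There are also safeguards. Under 7.0, reductions and interruptions after cycle 1 are at the Principal Investigator's discretion, interruptions beyond 5 days should be discussed with that investigator, and those beyond 21 days lead to withdrawal unless approved. Section 6.6 allows removal for safety. These make uncoordinated dosing less likely; they do not say which dose is right.

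**Conclusion.** The inconsistency is real, and confined to patients whose capecitabine was already reduced for another toxicity. The firm part is grade 4: 500 or 375 after one earlier cut, with nothing in the protocol to choose between them, and an unchanged 500 or a barred 250 after two. The grade 3 part is a conflict in wording that 7.0 resolves if it is read as an overriding cap; 7.2.6 should then say that those steps cannot be reached.

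This rests on counting capecitabine modifications only. A third one exceeds the 7.0 limit whether 7.0 counts per drug or per patient. The statement that 7.0 is silent after one earlier cut assumes that CB-839 reductions are not added in as separate modifications. Section 7.1.3 calls for one at grade 3 or higher bilirubin, and 7.0 does not say how to count it.

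A reader might infer damage to the efficacy analysis. None is shown: the path is rare and nothing here bears on sample size or power. This is a cheap improvement to a safety dosing rule.

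**What to change.** Change 7.2.6 only. Delete both re-basing sentences and write:

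- *Grade 3:* Earlier capecitabine reductions for any toxicity count; resume at the next lower level in 7.2.1 (75%, then 50% of the original starting dose).
- *Grade 4 (replacing the present instruction):* For a first grade 4 event in a patient above 50% of the original starting dose, resume directly at 50% of the original starting dose; discontinue for any subsequent grade 4 event.
- *Both:* A patient already at 50% of the original starting dose who has a further grade 3 or 4 hyperbilirubinemia event discontinues capecitabine permanently; the 7.0 limit of 2 dose modifications applies throughout.

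The grade 4 case needs its own sentence. A single next-level rule for both grades would send an unreduced patient to 75% after a grade 4 event. The last sentence is needed for a patient brought to 50% by one grade 4 event: that is only one modification, so 7.0 alone would not say what follows.

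Whether 7.0 counts per drug or per patient can stay with the sponsor; this wording works with either.

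The cost is amendment text, with no new procedures and no change to hold times. The downside is that some patients would stop who, on a literal reading of 7.2.6, could have continued at 37.5% or 25% of start. The grade 4 dose after one earlier cut is also settled at 500, the higher of the two.
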